5.1 Flow Chart

The work flow of study procedures in this trial was designed to be as close to routine clinical care as possible to represent daily routine clinical care in an optimal way.

Figure 2: Study flow chart

All enrolled and measured patients will be followed for 1 month after end of index thyroid surgical procedure or until withdrawal of consent.

6. Selection of Patients

6.1 Informed Consent

A signed informed consent form, written in accordance with country-specific applicable data privacy acts, the Declaration of Helsinki (Appendix V) and applicable laws for research using medical devices, and approved by the responsible Ethics Committee (EC), will be obtained from every patient prior to any study-related procedure. It will be explicitly explained to patients eligible for the HEDOS study that their data might also be used within HEDOS II. All clinical data needed to evaluate the potential eligibility of a patient before study inclusion (pre-screening), e. g. recent laboratory results or other technical parameters, are to be performed during routine clinical care and are therefore not considered to be part of study related procedures.

An investigator will explain the nature, purpose and risks of the study and provide the patient with a copy of the patient information sheet. The patient will be given sufficient time to consider the study's implications before deciding to participate. In addition, it will be explained that the patient is free to leave the trial at any time without any disadvantage or loss of therapy quality.

Should there be any modifications to the protocol, such that this would directly affect the patient's participation in the study, e.g. a change in any procedure, an addendum to the informed consent form specifying the modification must be compiled and the patients who already gave informed consent must agree to sign this addendum indicating that they consent to further participate in the modified study.

A signed copy of the patient's informed consent form and any signed addendum to the informed consent form must be maintained in the study file on site. The patient's permanent medical records at the site should indicate the patient's study participation.

6.2 Study Population

6.2.1 Number of patients and definition of status

HEDOS will enrol and measure presumably 1,470 eligible adult patients and follow each of them for 1 month, assuming that 22 events of clinically relevant hemorrhage within 48 hours following thyroid surgery will be observed.

A patient is considered as enrolled into the trial according to regulatory requirements as soon as he has **signed** the informed consent form. Documentation of any patient data in the e-CRF is permitted only after the patient signs the informed consent form. All enrolled patients will be reported and will be part of the safety population. Enrolled patients who are subsequently not measured with thyroid surgery as defined in the study protocol will not count to the number of enrolled patients needed, and will be replaced as soon as absence of thyroid surgery has been determined and documented in the clinical files of the patient.

A patient is considered as **screened** as soon as inclusion and exclusion and other eligibility criteria have been checked and documented in the e-CRF after the patient signed the informed consent form. Screened patients who are subsequently not measured with thyroid surgery as defined in the study protocol will not count to the number of enrolled patients needed, and will be replaced as soon as absence of thyroid surgery has been determined and documented in the clinical files of the patient. These patients will be followed until date of determination of absence of thyroid surgery. If a screened patient is scheduled for index thyroid surgery after global end of the study or after termination of study participation of the corresponding study site his study participation will end at the corresponding date of administrative termination. A patient is considered as measured in the trial as soon as he is **enrolled and thyroid surgery** as defined in the study protocol was performed. All measured patients will be part of the ITD population. Measured patients will be followed according to study protocol.

The day of **enrolment** is **day 1 of study participation**, the **day of index thyroid surgery** as defined in the study protocol is **day 1 of follow-up** for primary and secondary endpoints of an individual study patient.

6.2.2 Inclusion criteria

- **I1.** Age ≥18 years.
- **12.** Indication for thyroid surgery (e.g. total thyroidectomy, subtotal resection, partial resection or lobectomy) in routine clinical care according to applicable medical guidelines using all adequate surgical approaches.
- **I3.** Signed informed consent.

All inclusion criteria have to be documented for source data review in the permanent clinical files of the patient at the site.

6.2.3 Exclusion criteria

E1. Intended use of drains.

6.2.4 Randomisation (Rx)

For this type of purely diagnostic trials no randomisation (Rx) into treatment groups is required (within-subject design). All patients passing in- and exclusion criteria and subsequent index thyroid surgery will receive the diagnostic IP and will be assessed.

7. Therapy

Within this purely diagnostic trial by study protocol no medical treatment is defined other than thyroid surgery as inclusion criterion. Indication for thyroid surgery, type of surgery performed (e.g. total thyroidectomy, sub-total resection, partial resection or lobectomy) and procedures before, during and after surgery are at the discretion of the treating physician in routine clinical care according to applicable medical guidelines and local policies, and are not defined in the study protocol. Therapies provided to study patients will be documented as required in the e-CRF.

7.1 Investigational medical product (IP)

The IP used within this study is ISAR-M THYRO[®], a diagnostic device of class IIb according to EU regulation 2017/745 for early detection of hemorrhage following thyroid surgery. The device uses a sterile disposable compartment pressure probe to be placed in the operating field at the end of thyroid surgery before wound closure. It will be connected to a wearable, external device fixed as a small box at the upper arm of the patient by a soft silicone bracelet. In case of surgery on both neck sides two pressure sensors have to be used but both connected to just one external device box.

The IP system consists of the following technical components:

- Thyro I KID (REF: TH-020101): The Key Instrument of pressure Detection (KID) is a sterile, disposable compartment pressure probe to be used with reusable parts of the IP system. It is an invasive probe with air chamber and connector for pressure absorption in surgery cavities. The upper end of the pressure probe (soft air chamber) is inserted into the thyroid compartment before closing the surgical wound. The sensor connector is plugged into a socket of the SON.
- Thyro I SON (REF: TH-010201): The Smart OperatioN (SON) is a unit for recording and displaying the sensor data, acoustic and visual alarm, storage of monitoring data and data transmission to the external

monitoring master (MOM) via wireless communication. The SON is to be attached to the patient's upper arm using an accessory belt (REF: TH-010301). One or two KIDs shall be connected to the SON.

- Thyro I MOM (REF: TH-010401): The MOnitoring Master (MOM) is a medical device app (CRI_1.0.1, version number V3.4A) pre-installed at a handheld with a protective cover to display patient files, trend analyzes, statistics and with acoustic and visual alarming function. It has a wireless connection to the SON for data exchange and for control and alarming nearby the patient.
- Thyro I DOCK (REF: TH-010501): The Device Of Charging Key (DOCK) is the storage and charging unit for both, the MOM and the SON. The unit will be located at medical staff. The DOCK is connected to the power by an AC-DC reliable green medical adaptor (REF: TH-010601).

The IP will be used within the study for continuous measurement of pressure values and their digital documentation with alerts and pressure display off. Potential risks of this equipment are local infections at the suture or in the surgical area. However, pressure sensor catheter and suture are protected by adequate dressing and the sensor will be removed completely about 48 hours after wound closure without reopening the suture.

The IP (without market approval) shall be kept in a locked location with limited and controlled access only for authorized persons at the study site. It will only be used for patients enrolled into the study.

7.1.1 Intended use of the IP

The system is installed at the end of the operation and runs for up to 48 hours. The use of the system allows timely re-operation and haemostasis even in the symptom-free stage and allows a data based decision for a necessary rescue operation. The IP is light weighted, battery operated and can be carried by the patient on the body.

In the study version of the IP all pressure values measured by the pressure probe are recorded and analyzed. If the specified pressure points are exceeded, this event is stored in a log file, but is not used to trigger an alert that can be detected by the user. This means that there is no pressure display on SON or MOM, no trend display on the MOM and no pressure alert on both devices. In addition, no pressure alert messages are emitted via SMS.

Based on the saved pressure file and the event log file, the compartment pressure history can be analyzed retrospectively over the entire duration of the observation and the correctness of the recorded pressure alerts can be traced and checked.

7.1.2 Technical and functional features of the IP

A detailed description is given in Appendix VI.

7.1.3 Information on traceability and use of the IP

For accountability of technical components of the IP system, the following information will be documented and traced by the study sites in the e-CRF:

- a) information on all components ever received at the study site (identification by serial or lot numbers, expiry date if applicable, quantity, and date of receipt),
- b) information on usage of the IP including, if applicable, identification of corresponding study patient, and date or dates of use and date of return from study patient,
- c) where applicable, information of the disposal of IP as per instructions of the sponsor,
- d) information on return of unused, expired, or malfunctioning IPs.

Summary reports on accountability and use are available within the e-CRF for individual study sites.

In addition to documentation by the study sites, the sponsor will document and trace IP devices ever shipped to study sites or returned from them.

7.2 Unblinding

The HEDOS trial is a single-arm study without blinded treatment or procedure groups. Thus, unblinding procedures for investigators are not applicable. The measurements of the IP are not visible to investigators and will be kept secret until the end of the trial.

7.3 Auxiliary Medical Therapies

All medical therapies used within HEDOS comprise marketed products used in line with market authorisation and represent SOC, therefore no auxiliary medical therapy is defined.

7.4 Concomitant Medication

All patients will be provided with medical care and accepted evidence-based medication in accordance with applicable recent guidelines. Concomitant medication will be documented by generic name in the e-CRF.

7.5 Post-study Treatment

Within this purely diagnostic trial no post-study treatment is defined. Any medical therapy within or after the individual end of participation in this trial represents the individual decision of the treating physician and has to be in line with current medical guidelines and local policies. No therapies are specified in this study protocol.

8. Adverse Event (AE) recording

Within this purely diagnostic trial no medical treatment is defined other than thyroid surgery. The diagnostic IP is used as external tool outside the body. The catheter-based pressure sensor is introduced during the surgical procedure into the surgical field just before wound closure. Results of clinical studies with comparable catheter-based pressure sensors yield very low to negligible rates of adverse events caused by the sensor. All other medical devices and medication used in HEDOS comprise only marketed products used in line with market authorisation and SOC as described in applicable medical guidelines. Thus, adverse events are expected to occur in similar clinical manifestations and at a comparable rate as the known adverse events of the applied thyroid surgery in routine clinical care. The trial is therefore assessed as representing a low structural risk.

8.1 Adverse Events (AEs)

Is any untoward medical occurrence, unintended disease or injury, or untoward clinical signs (including abnormal laboratory findings) in subjects, users or other persons, in the context of a clinical investigation whether or not related to the IP. This definition includes events that are anticipated as well as unanticipated events and those occurring in the context of a clinical investigation related to the IP or the procedures involved. For users or other persons, this definition is restricted to events related to IPs.

Any surgery procedure or other intervention irrespective of its relation to the IP or the index thyroid surgery is an AE and has to be documented.

A newly diagnosed concomitant disease is also considered an AE.

All AEs occurring from enrolment until end of follow-up of each study patient will be documented by study site personnel in the e-CRF immediately after study site personnel's awareness of the event, and will subsequently be assessed by the sponsor and reported to authorities involved.

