4.2 Secondary Endpoint Parameters

Secondary endpoint parameters are defined as:

- EP3. Safety of the use of the diagnostic IP by means of adverse events within 1 month following thyroid surgery.
- EP4. Sensitivity and specificity of the IP for detection of clinically relevant hemorrhage within 48 hours following thyroid surgery in a three-level decision system using 10 and 20 mmHg of pressure as cutoffs compared to detection in routine clinical care.
- EP5. Positive and negative predictive values of the IP for detection of clinically relevant hemorrhage within 48 hours following thyroid surgery using the two-level and the three-level decision system compared to detection in routine clinical care.

Clinically relevant hemorrhage and serious adverse events will be adjudicated by an independent Endpoint Review Committee (ERC) according to standardised definitions [7] given in the ERC charter. Outcome death in follow-up will be assessed as equivalent endpoint to clinically relevant hemorrhage.

Parameters relevant for endpoints within the test treatment study (stage 2) are collected within HEDOS study (diagnostic accuracy study, stage 1), too, e.g. clinical symptoms triggering surgical intervention of a suspected post-operative hemorrhage detected in routine clinical care, time to clinical or technical alerts, surgical interventions which did not show post-operative hemorrhage needing intervention.

5. Study Design

In general, the development of a diagnostic test is structured in four phases [1]. In phase I, the functionality and safety of the diagnostic test is examined. In phase II, the diagnostic test is applied to individuals with known disease status to define the cut-off value. Phase III evaluates the diagnostic accuracy based on the pre-defined cut-off value in patients with unknown disease status. Phase IV aims to determine patients' benefit of the test-treatment combination. Hence, the last two phases of the development process are combined. Two single studies are planned to be combined into a phase III/IV seamless design in which a confirmatory phase III diagnostic accuracy study (stage 1) and a subsequent phase IV cluster randomised test treatment study (stage 2) are connected to each other and data from the diagnostic accuracy study will also be used for the randomized test treatment study.

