8.2 Serious Adverse Events (SAEs)

A SAE is any untoward medical occurrence that

- led to death,
- Ied to serious deterioration in the health of the subject, that either resulted in
 - > a life-threatening illness or injury, or
 - > a permanent impairment of a body structure or a body function, or
 - > hospitalisation or prolongation of patient hospitalisation, or
 - medical or surgical intervention to prevent life-threatening illness or injury or permanent impairment to a body structure or a body function,
 - > a chronic disease,
- Ied to foetal distress, foetal death or a congenital abnormality or birth defect.

More than one of the above criteria can be applicable to each event.

These characteristics/consequences have to be considered at the time of the event. For example, regarding a life-threatening event, this refers to an event in which the subject was at risk of death at the time of the event. It does not refer to an event which hypothetically might have caused death if it were more severe.

NOTE:

The following overnight hospitalisations are not considered SAEs:

- Not urgent hospitalisation for
 - > a condition existing before signing consent, or
 - > a procedure required by the study protocol without serious deterioration in health.
- Elective inpatient hospitalisation (e.g. surgery) verifiably planned before signing consent.
- Any overnight hospital stay required only for diagnostic procedure (e.g. in a sleep laboratory).

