12.1.3 Analysis of the secondary endpoints

The positive and negative predictive values are reported descriptively with 95%-logit confidence intervals. Their calculation follows from the analysis method chosen for the primary endpoints. To estimate predictive

values with the mixed binary logistic regression model, the true disease status represents the dependent variable. The test results are included as fixed effects and again a random-intercept is estimated for each centre. Positive predictive value is estimated via the calculation of the marginal mean for a test positive result. False-negative rate, which is the counter probability of the negative predictive value, is estimated via the calculation of the marginal mean for a non-diseased individual. Two-sided 95%-logit confidence intervals with pvalues are reported.

Other secondary endpoints, including safety endpoints, will be analysed descriptively.

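### Section 8.1 classes every surgery or intervention as an adverse event in itself, so EP3's event counts take in planned procedures and can list a bleed and its re-operation separately

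*Protocol*

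**What the plan says.** Section 8.1 of the protocol opens with the usual definition. An AE "Is any untoward medical occurrence, unintended disease or injury, or untoward clinical signs (including abnormal laboratory findings) in subjects, users or other persons", whether or not it is related to the device. A separate sentence then states: "Any surgery procedure or other intervention irrespective of its relation to the IP or the index thyroid surgery is an AE and has to be" recorded. The next sentence names a newly diagnosed concomitant disease as an AE too. On the recording window, 8.1 says: "All AEs occurring from enrolment until end of follow-up of each study patient will be documented by study site personnel in the e-CRF".

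Section 8.2 lists medical or surgical intervention among the outcomes that make an untoward occurrence serious. Its note removes some overnight stays from serious adverse event (SAE) status, among them "Elective inpatient hospitalisation (e.g. surgery) verifiably planned before signing consent". Section 8.4 lists the interventions performed as one item of the SAE record, next to onset, intensity and outcome.

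EP3 in section 4.2 is "Safety of the use of the diagnostic IP by means of adverse events within 1 month following thyroid surgery". Section 12.1.3 adds: "Other secondary endpoints, including safety endpoints, will be analysed descriptively". The introduction to section 8 gives the expectation that "adverse events are expected to occur in similar clinical manifestations and at a comparable rate as the known adverse events" of thyroid surgery in routine care.

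**The concern.** A procedure is normally the response to an event. Section 8.1 makes it an event, requires nothing untoward to have happened, and has no exception for a procedure arranged before consent or for one that treats an AE already recorded.

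EP3 has no test or threshold, so the AE count itself is the safety result. A count that mixes conditions with the procedures used to treat them is hard to read against the protocol's own expectation of rates similar to routine care. The wording also governs what staff at about 50 sites enter. If some enter one record for a re-operated bleed and others two, an analyst cannot reliably separate them later unless each procedure was linked to a condition at entry.

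**Working it through.** **Step 1. The provisions side by side.**

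| Section | Status of a procedure |
|---|---|
| 8.1, general definition | Not an AE unless something untoward occurred |
| 8.1, added sentence | An AE in itself, whatever its relation to device or index surgery |
| 8.2, seriousness criteria | A consequence that makes an event serious |
| 8.2, note | An elective inpatient stay planned before consent is not an SAE; AE status is not addressed |
| 8.4 | An item in the record of an event |

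The added sentence in 8.1 differs from every other row. Nothing in 8.2 or 8.4 says that it is overridden.

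**Step 2. Apply the literal text to two patients.**

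- *Planned procedure.* A patient has an unrelated elective procedure, arranged before consent, within the month after thyroid surgery. It is an AE under the added sentence. The 8.2 note can keep the stay from being an SAE but does not remove AE status. A patient with no untoward event therefore enters EP3.
- *Re-operated bleed.* The bleed is an AE under the general definition and the re-operation is an AE under the added sentence. No passage tells the site to merge them and none tells it to enter both. Two entries are therefore permitted but not required.

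**Step 3. Size of possible double entry.** Inputs: 1,470 patients, 1.5% prevalence (section 12.2) and 22 expected bleeds (section 6.2.1).

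- Plan's own figure: 1,470 × 0.015 = 22.05, which reproduces the stated 22.
- One entry per bleed: about 22 bleed-related entries.
- Two entries per bleed: 2 × 22 = 44.
- Excess: 44 − 22 = 22 entries; 22 / 1,470 = 1.5 per 100 patients.
- Over the bleeding range of 0.6% to 4% quoted in section 3.1: 1,470 × 0.006 = 8.8 and 1,470 × 0.04 = 58.8, so about 9 to 59 extra entries if every bleed were re-operated and entered twice.

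**Step 4. Patient-level count.** A patient with a re-operated bleed already has an AE. A second entry adds 0 to the number of patients with at least one AE. A planned procedure in an otherwise event-free patient adds 1.

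**Step 5. Planned procedures.** The protocol gives no rate for them, so no figure is offered.

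**The case against.** The best reply is that the protocol, read as a whole, points to one event per bleed. Section 8.4 makes the intervention an item of the SAE record, 8.2 makes it a seriousness criterion, and 4.1 defines the bleed by the surgical intervention. EP3 does not say whether events or patients are counted, and section 12 leaves coding guidelines and output tables to the SAP. No test depends on EP3. Broad capture also has a purpose: re-intervention defines the reference standard, and section 4.2 wants re-operations that showed no hemorrhage needing intervention recorded for stage 2.

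Much of this stands. Double entry is a possibility, not something the protocol states, and capture of every re-operation must be kept. It does not remove the point, because the literal rule still makes planned procedures AEs, and an SAP cannot reliably repair records that sites entered in different ways.

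Three stronger readings are tempting and not supported:

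- *The index operation is itself an AE, so every patient has one.* The sentence uses the index surgery as the reference to which other procedures may or may not be related. Section 9.2.2 asks sites to record those events of the index stay that meet AE criteria, which presupposes that the operation is not one of them.
- *SAEs are doubled.* Under 8.2 the re-operation is what makes the bleed serious. No text calls for a second SAE or a second adjudication.
- *Harms of the device are diluted.* Section 8.3 has relatedness to the device assessed separately, and device effects have their own categories.

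The comparable-rate statement in section 8 is a risk rationale, not a planned comparison. Only the interpretability of the count is at stake.

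**Conclusion.** The point holds as a minor inconsistency. Section 8.1 labels procedures as AEs, conflicts with 8.2 and 8.4, and excludes no planned procedure at AE level. Applied as written, EP3's event counts include planned procedures without an untoward event and can include up to about 22 extra bleed-related entries (1.5 per 100 patients). That upper figure assumes the planned 1.5% prevalence, separate entry of every bleed and its re-operation, and counting of events rather than patients. It falls to zero if sites enter one record per bleed or if EP3 counts patients.

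EP1, EP2, alpha, power and the device-relatedness assessment do not change.

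**What to change.** Replace the added sentence in 8.1 so that it agrees with 8.2 and 8.4. It should state that:

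- every surgery or intervention after enrolment is documented in the e-CRF, including every re-operation of the neck whether or not hemorrhage is confirmed;
- the AE is the underlying condition, and the procedure is recorded as the action taken for it;
- the index surgery, and procedures planned before consent without deterioration of the condition, are documented but not counted as AEs in EP3.

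The first item matters because the current sentence is the explicit rule that every surgery be documented. It must not be lost, since re-interventions define the reference standard and feed stage 2.

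The cost is one paragraph and one e-CRF completion instruction. Sites must link each procedure to a condition, which adds some queries where no reason is given.
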